## **9.0 CONSENT PROCESS**

Following recruitment and screening, the potential participant will be given a copy of the informed consent form (ICF) in-person or via postal mail or e-mail for review. There is no required timeline between their receipt of the ICF and deciding whether or not to participate. Participants will be encouraged to read the consent and take their time to decide.

Informed consent will take place on the MUSC campus or through telehealth (eConsent) by trained research staff in a private area. If consenting through telehealth using an IRB-approved electronic/online platform (i.e. REDCap or musc.doxy.me; all future references to an “electronic/ online platform” hereafter refer to these), the research staff will first confirm that participants have the appropriate technology to complete the electronic consent process. In the case of eConsent, the participant will be asked to locate a private and interruption-free environment in order to complete the appointment.

The study PI, a Co-I, or other qualified research staff will obtain informed consent. The research staff member will ensure that the Participant comprehends the study purpose and procedures, is provided with ample opportunity to ask questions. Participants will verbalize their consent to participate, sign the informed consent and HIPAA documents, and will be given a copy for their records. If consenting through an electronic/online platform, research staff will use a secure system for electronic or digital signature and will provide subjects with a copy for their records.

## 10.0 STUDY DESIGN / METHODS

Participants will complete 4 sets of procedures: Eligibility Assessment, Study Visit (Day 0), Cue Reactivity Ecological Momentary Assessment (CREMA; Days 1-7), and the Trier Social Stress Task (TSST; Day 8). *With the exception of the procedures within Study Visit 0, all of the procedures described here are IRB-approved for the parent study (Pro# 00081360):*

Procedure: **ELIGIBILITY ASSESSMENT**

Setting: Either or a combination of electronic/online platform or in-person delivery (at the Addiction Sciences research space at [name]), depending on participant preference  
 Personnel: Research staff  
 Duration: 1.5 hours  
 Description: Following consenting, trained research staff will administer the following semi-structured interviews and questionnaires to ascertain that he/she meets the clinical eligibility criteria using measures that are already approved and being administered in the parent study.  
 Measures: Clinical Assessments and Substance-Related Questionnaires

Mini-International Neuropsychiatric Interview (MINI)

Marijuana Use Questionnaire

Time Line Follow-back (TLFB)

Inventory of Drug-Taking Situations (IDTS)

Perceived Stress Scale (PSS)

Adverse Childhood Experiences (ACE) Questionnaire

Personal History (May be done at Eligibility Assessment or Day 0: Study Visit)

Subject Demographics, Medications, and Health History: All participants will complete 3 brief questionnaires from the National Alzheimer’s Coordinating Centers Uniform Dataset (NACC-UDS) to capture all relevant personal and medical history variables.

Geriatric Depression Scale: A 30-item self-report measure of depression severity.

Menstrual, Reproductive, and Hormone Therapy History: Female participants will complete a brief questionnaire based on the PhenX Toolkit. These measures were administered in NIH-funded lifespan studies including the Women’s Interview Study of Health and the Study of Women Across the Nation.

Mobile Device Proficiency Questionnaire-16 (Roque & Boot, 2018): This brief measure will index participants’ facility with mobile technology. Researchers will use this information to triage participants in need for more assistance with CREMA.

Procedure: **DAY 0: STUDY VISIT**

Setting: Center for Biomedical Imaging (CBI; [name]) and Research Nexus

Personnel:	Research staff
Duration:	1 hour (at CBI) and 2 hours (at Nexus)
Description:	
Female participants who are of childbearing potential will first undergo a pregnancy test. A negative pregnancy test is required to proceed with all other study procedures. The breathalyzer test [alcohol] and saliva drug test [THC, cocaine, amphetamines, opioids, benzodiazepines] will be administered to ensure sobriety prior to initiation of all procedures. If breathalyzer or saliva test result is inconclusive, test will be repeated. If second test is also inconclusive but patient self-reports abstinence and does not exhibit signs of impairment, patient may proceed with study visit. Participants will also provide a urine sample, which will be tested for the presence of cocaine, opiates, barbiturates, benzodiazepines, and stimulants. The urine sample will also be quantitatively analyzed for cannabinoids and creatinine to characterize past week cannabis use. If results of the breathalyzer, saliva drug test are clear, then brain MRI, vitals, fasting blood collection, personal history questionnaires, and neurocognitive testing will be conducted ideally within the same day to collect the data for the following outcome variables:
 
 
• ADRD risk based on imaging and blood-based biomarkers (see below)
 
• American College of Cardiology/American Heart Association (ACC/AHA) 10-year risk of heart disease/stroke (Goff et al. 2013) to quantify vascular disease risk.
 
• Global Cognitive Ability (GCA) derived from neurocognitive testing.
 
 
Paper-and-pencil and computerized cognitive tests will be administered to each participant by trained research staff. Testing will include ample time for breaks. Verbal responses to some tests will be recorded using a digital voice recorder to facilitate scoring accuracy. Audio files will be uploaded onto a secure server and labeled with the participant ID. The files on the digital voice recorder will be deleted after uploading.
 
Participants will also receive a study iPhone (if they do not have or wish to use their own) and will receive training on how to use it for the CREMA sessions. Female participants will receive a kit and instructions for providing saliva samples in conjunction with the CREMA sessions.

Measures:	
ADRD MRI-based biomarkers
 
Medial temporal/hippocampal atrophy and leukoaraiosis volume: These metrics will be obtained using established image analysis pipelines in the PI's laboratory. Structural and functional MRI sequences will be acquired to obtain these and other preliminary data for future studies.
 
Health Variables
 
Vitals (blood pressure, pulse, oxygenation rate, height, weight)
 
Total lipid panel (from blood plasma)
 
High-sensitivity C-reactive protein (from blood plasma)
 
ADRD blood-based biomarkers
 
AB40, AB42, pTau-181, Glial fibrillary acidic protein, Neurofilament light: Measurements will be obtained from blood plasma and assayed through the vendor Quanterix which uses Simoa® technology for sensitive biomarker detection.
 
Neurocognitive testing
 
Version 3 of the NACC-UDS neuropsychological battery (Weintraub et al., 2018): This is the 40-minute test battery that produces the scores needed to generate the Global Cognitive Ability factor.
 
NIH Toolbox – Cognition Battery: We will additionally administer this 20-minute computerized battery to obtain complementary data on cognitive functioning for preliminary data/future research.

Procedure:	DAYS 1-7: CREMA
Setting:	At home, with study-issued or own iPhone
Personnel:	Research staff will be available should participants need assistance

Duration: 3-4 minutes per session, 3 sessions per day

Description: The Cue Reactivity Ecological Momentary Assessment (CREMA) is a cue reactivity assessment in which photographic stimuli are presented multiple times per day on a mobile electronic device. Auditory alarms will alert participants to complete three, randomly scheduled CREMA sessions per day (session = 3-4 mins). Alarms will be distributed over a participant-selected 12-hour period, divided into three, 4-hour blocks with a minimum time of 30 minutes between alarms/CREMA sessions.

Measures: Female participants will be asked to give a saliva sample every morning they complete CREMA. Female participants will be given instructions on how to collect and store a saliva sample on Day 0. They will complete the sample within 30 minutes of waking up and before eating or drinking. All participants will complete the pre- and post-cue subjective measures of craving and stress, obtained as follows. At the start of each CREMA session, participants will be asked to provide ratings on craving, mood, and stress using a modified version of the Within Session Rating Scale (WSRS; Childress et al., 1986). This visual analog scale is anchored with adjectival modifiers. The scale includes items assessing anxiety, stress, irritability, and craving. If the session is one of the two daily picture assessments, next a photograph (either stress-related or neutral) will be presented and the participant will be instructed to look at it carefully for 10 seconds. Each picture cue will appear only once during the study. An alarm will sound at the end of each trial, after which participants will complete a post-cue WSRS assessment, ratings of how carefully they looked at the photographs and their distraction level during each trial, and data on their cannabis use since last assessment. If the session is only collecting ambient stress and craving, immediately after the WSRS the participants will be asked to record data on cannabis use since the last assessment session.

**Procedure: DAY 8: TSST**

Setting: Addiction Science research space at [name]

Personnel: Research staff

Duration: 3 hours

Description: On day 8, participants will be instructed to arrive at 11:00am on the day of the TSST, and to avoid caffeinated beverages on the test day since caffeine can inflate reactivity to the stressor. Upon arrival, female participants will provide study staff with their saliva samples from the past 7 days. Women of childbearing potential will undergo a pregnancy test. All participants will be breathalyzed and undergo a saliva drug test to ensure sobriety prior to initiation of TSST. If breathalyzer or saliva test result is inconclusive, test will be repeated. If second test is also inconclusive but patient self-reports abstinence and does not exhibit signs of impairment, patient may proceed with study visit. Participants will also provide a urine sample, which will be tested for the presence of cocaine, opiates, barbiturates, benzodiazepines, and stimulants. The urine sample will also be quantitatively analyzed for cannabinoids and creatinine to characterize past week cannabis use.

Research staff will administer the Time Line Follow-back (TLFB) interview to assess marijuana use, with the time window being from the last TLFB (during the Eligibility visit) to today/Day 8.

The participant will provide a saliva sample to test for progesterone levels.

At 11:30am a blood pressure cuff will be placed on the participant's arm. Questionnaires (Marijuana Craving Questionnaire [MCQ], Mood, State-Trait Anxiety Inventory [STAII] questionnaires), hormonal (cortisol), and physiologic measures (blood pressure and heart rate) will be collected twice, once at 11:40am and again at 11:55am.

At 12:00pm, the participant will be told that (s)he will give a speech and perform an arithmetic task. The topic of the speech will be why (s)he should be hired for a particular job (the individual's "dream job"). The participant will deliver the speech as though speaking to a group of potential employers. The experimenter then tells the participant that (s)he has 5 minutes to prepare the speech, and then starts the countdown clock (placed in view of the

individual). The experimenter leaves the room to allow the participant to prepare. Five minutes later, 3 individuals unfamiliar to the participant (the audience) enter the room and are seated; the individual will be instructed by one audience member to stand and begin his/her prepared speech (without notes). The speech will be delivered for 5 minutes. If the individual pauses, (s)he will be instructed to continue.

At the end of the speech task, the individual will be instructed to serially subtract 13 from 1,022 as quickly and accurately as possible for 5 minutes, at the end of which time, the spokesperson will instruct the individual to stop and be seated, and the audience leaves the room. At this point, a third saliva sample will be collected (for cortisol) and physiological (blood pressure and heart rate) and questionnaires (MCQ, Mood, STAI) obtained. Measurements will also be obtained at 5-, 30-, and 60-minutes post-task.

Measures: Physiological (progesterone [1 sample], cortisol [6 samples], blood pressure, heart rate) measures and subjective (craving, stress) measures (MCQ, Mood, and STAI).

## DAY 8: TSST

	
 
▪ SCREEN: Breathalyzer, Saliva drug screen, Urine drug screen
 
▪ SAMPLE: Collected urine will also be tested for cannabinoids and creatinine (quantitative)
 
▪ INTERVIEW: TLFB update
 

11:00	
11:30	
 
▪ PHYSIO: Place blood pressure cuff on arm
 
▪ SAMPLE: Collect salivary progesterone (1 of 1 sample, label "<studyid>_prog")
 

11:40	
1st of 6 measurements:
 
 
▪ PHYSIO: Measure HB/BP
 
▪ QUESTIONNAIRES: MCQ, Mood, STAI on iPad
 
▪ SAMPLE: Collect salivary cortisol, label "<studyid>_11:40", store in fridge
 

11:55	
2nd of 6 measurements:
 
 
▪ Bring supplies for Trier into the room: pen, paper, timer, clipboard
 
▪ PHYSIO: Measure HB/BP
 
▪ QUESTIONNAIRES: MCQ, Mood, STAI on iPad
 
▪ SAMPLE: Collect salivary cortisol, label "<studyid>_11:55"
 

12:00	
 
▪ Read participants the script and set a 5-minute countdown clock.
 
▪ Leave the room and place cortisol <studyid>_11:55 sample in the fridge.
 
▪ Prepare the audience
 

12:05	
 
▪ When timer goes off, enter the room
 
▪ Collect the participant's pen and paper and tell the participant "Members of the research team will be with you shortly"
 
▪ 3 audience members enter the room, and 1 tells the participant to begin
 
▪ The speech must be for 5 minutes; If the participant pauses they will be prompted to continue
 

12:10	
 
▪ Ask the participant to serially subtract 13 from 1,022 as quickly and accurately as possible for 5 minutes
 
▪ Then participant will be asked to be seated
 

12:15	
 
▪ Audience will leave the room and you will immediately go in for the next two data collections
 
▪ Bring 2 saliva tubes, iPad, data collection sheet and bp cuff
 
▪ 3rd of 6 measurements:
 
▪ PHYSIO: Measure HB/BP
 
▪ QUESTIONNAIRES: MCQ, Mood, STAI on iPad
 
▪ SAMPLE: Collect salivary cortisol, then label "<studyid>_12:15"
 

12:20	
4th of 6 measurements:
 
 
▪ PHYSIO: Measure HB/BP
 
▪ QUESTIONNAIRES: MCQ, Mood, STAI on iPad
 
▪ SAMPLE: Collect salivary cortisol, label "<studyid>_12:20", and store both <studyid>_12:15 and <studyid>_12:20 in fridge)
 

12:45	
5th of 6 measurements:
 
 
▪ PHYSIO: Measure HB/BP
 
▪ QUESTIONNAIRES: MCQ, Mood, STAI on iPad
 
▪ SAMPLE: Collect salivary cortisol, label "<studyid>_12:45", store in fridge)
 

1:15	
6th of 6 measurements:
 
 
▪ PHYSIO: Measure HB/BP
 
▪ QUESTIONNAIRES: MCQ, Mood, STAI on iPad
 
▪ SAMPLE: Collect salivary cortisol, label "<studyid>_1:15", store in fridge)
 

DEBRIEF	
 
▪ Let the participant know that the task is meant to be stressful and that the people were not actually judging them
 

DISCHARGE	
 
▪ If patient's craving is significantly elevated (20% higher than baseline), find qualified staff to talk to them prior to discharge. Have the clinician write a progress note to document their intervention.
 
▪ If the patient's craving not elevated: thank participant and discharge
 

**Participant Compensation:** Participants will be compensated as follows:

Eligib. Assessment:	\$50
Study Visit (Day 0):	
\$55 (for brain MRI)
 
\$40 (for vitals and provision of blood and saliva samples)
 
\$50 (for neurocognitive testing)

CREMA (Days 1-7):	
\$105 (max, at a rate of \$5/completed CREMA session [21 total sessions])
 
\$70 (max, at a rate of \$10/completed saliva sample [7 total samples] – females only)

TSST (Day 8):	
\$50
 
Total: \$350 per participant upon the completion of all procedures (males only)
 
Total: \$420 per participant upon the completion of all procedures (females only)

Participants will receive payments after completion of each procedure as outlined above. Payments will be made using ClinCards. In the event that the Eligibility Assessment is initiated via telehealth, the ClinCard will be mailed to the participant after completing the session.

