**Power and Sample Size.** This is a pilot study for the purposes of generating preliminary data to establish feasibility and power analyses for subsequent grants. The proposed analyses will provide effect sizes with which to generate sample size estimates. It will also provide us preliminary data for the acceptability of "real world" assessment of stress via CREMA in a population for whom proficiency with mobile technologies is diminished. Importantly, with our detailed assessment of menstrual, reproductive, and menopausal history, we will be able to meaningfully characterize hormonal influences on the hypothesized effects among women.

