## **15.0 RISKS TO SUBJECTS**

*Risk of physical discomfort associated with venipuncture.* Minimization: Participants may experience a slight pinch in their arm when the blood sample is taken, and subsequent slight bruising at the venipuncture site. While these effects commonly occur during this fairly routine procedure, these are transient and unlikely to cause persistent discomfort. Participants will be informed of this risk prior to the venipuncture to enhance their preparedness.

*Risk of psychological discomfort while completing substance use and psychiatric assessments.*

Minimization: These are all non-invasive, should add no risk, and have been used without difficulty or any adverse events in prior studies. Some participants may feel uncomfortable disclosing personal thoughts and feelings. All study participants will be closely monitored for psychiatric and medical stability. All sessions will be conducted under the supervision of experienced personnel. If crisis intervention is necessary, senior staff will be available to evaluate the subject and provide an intervention or referral. If hospitalization is indicated, the patient will be hospitalized through the Center for Drug and Alcohol Programs at MUSC or an appropriate referral will be made. All participants will be fully informed that they may withdraw from the study at any time without penalty. A referral to a mental health provider will be given if the participant requests it.

*Risks of stress induction procedures:* There is a small risk of increased stress or cannabis craving as a result of the TSST and CREMA procedures; however, it will likely not differ substantially from the reactivity elicited by stimuli commonly encountered in the day-to-day environment of study participants. Participants that report sustained significant stress or craving after the laboratory session will be provided a debriefing to address symptoms.

*Risk of psychological discomfort associated with neurocognitive testing.* Minimization: Neurocognitive testing is safe and non-invasive. It is possible, though unlikely, that participants may experience anxiety or distress during testing. If any of the tasks or questions elicit undue discomfort, participants will be encouraged to take breaks and will be reminded that they can discontinue testing or the study at any time. A referral to a mental health provider will be given if the participant requests it.

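### The Day 8 discharge step acts on craving alone, while Section 15.0 promises a symptom debriefing for lasting stress as well as craving

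*Combined protocol and SAP*

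**What the plan says.** Four places in the combined protocol and SAP bear on the end of the TSST visit.

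- **Section 10.0, Day 8 schedule, Discharge row.** The trigger is craving "20% higher than baseline), find qualified staff to talk to them prior to discharge", followed by a progress note from the clinician. If craving is not elevated, the instruction is to "thank participant and discharge".
- **Section 10.0, Day 8 schedule, Debrief row.** This comes just before discharge and has no condition attached, so it applies to everyone: "Let the participant know that the task is meant to be stressful and that the people were not actually judging them".
- **Section 15.0, paragraph on stress induction.** "Participants that report sustained significant stress or craving after the laboratory session will be provided a debriefing to address symptoms".
- **Section 10.0, Day 8 description.** The pre-task questionnaires and physiological measures "will be collected twice, once at 11:40am and again at 11:55am". After the end-of-task reading, "Measurements will also be obtained at 5-, 30-, and 60-minutes post-task". The visit collects "subjective (craving, stress) measures (MCQ, Mood, and STAI").

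**The concern.** The TSST is meant to produce stress, and Section 15.0 lists raised stress and raised craving as its risks. The working document for staff at the end of the visit is the Day 8 schedule, and its only decision point looks at craving. Stress, the state that the task is designed to provoke, has no decision point there.

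What is at stake is participant safety and the delivery of something the protocol says will be provided. A participant who is still distressed at the end of the visit, but whose craving has not gone up, falls into the branch that ends in discharge. The step applies to everyone who reaches Day 8, and Section 6.0 targets 50 completers (25 men and 25 women).

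**Working it through.** The plan gives no derivation for the 20% figure, and no sample size or error rate is involved. The check is therefore a comparison of texts, with two small pieces of arithmetic.

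**1. Are the ratings available before discharge?** The task ends at 12:15. Adding 5, 30 and 60 minutes gives 12:20, 12:45 and 1:15, which matches the schedule. The sixth and last set of MCQ, Mood and STAI ratings is taken at 1:15, and the Debrief and Discharge rows follow it. The description and the timetable agree, and current stress and anxiety ratings exist when the discharge decision is made.

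**2. What does each place require?**

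| State at the end of the visit | Day 8 Discharge row | Section 15.0 |
|---|---|---|
| Craving trigger met, with or without lasting stress | Qualified staff talk to the participant; progress note | Symptom-directed debriefing if the stress or craving reported is lasting and significant |
| Craving trigger not met, no lasting symptoms | Thank and discharge | Nothing further |
| Craving trigger not met, lasting significant stress reported | Thank and discharge | Symptom-directed debriefing |

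The third line is the gap. The schedule gives an affirmative instruction to discharge and contains no step that delivers what Section 15.0 describes.

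**3. Does the Debrief row fill the gap?** It tells the participant what the task was for and that nobody was judging them. It does not ask how the participant feels, refer to the 1:15 ratings or lead to any further action. The debriefing in Section 15.0 is conditional on reported symptoms and aimed at them. The two share a name but not a function.

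**4. Is the craving trigger fully specified?** The rule names no instrument or score. Two pre-task readings, 11:40 and 11:55, could serve as baseline. An illustration shows that the choice can matter. The scores are assumed, not taken from the documents, and 20% is read as a ratio: craving 50 at 11:40, 60 at 11:55, and 65 after the task.

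- Against 11:40: 65/50 − 1 = 30.0%, above 20%.
- Against 11:55: 65/60 − 1 = 8.3%, below 20%.
- Against the mean of the two, 55: 65/55 − 1 = 18.2%, below 20%.

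The result runs from 8.3% to 30.0% for one participant. This is a missing detail that would be a minor matter by itself. It is worth settling because the same row has to be edited anyway.

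**The case against.** The strongest reply is that the two places do different jobs. The schedule is a staff checklist with a score trigger, and Section 15.0 is a commitment that starts from what the participant reports. Neither forbids what the other requires, and staff who know both can honour both. Every participant also gets the explanatory debrief, which is aimed at stress. Section 15.0 calls the stress risk small and, under its heading on substance use and psychiatric assessments, provides for monitoring of all participants, experienced supervision of all sessions and senior staff in a crisis.

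Much of this stands. A reader might infer that the two sections contradict each other. The documents do not support that, because adding one step satisfies both. The general safeguards also make an unnoticed serious reaction less likely.

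A reader might also infer that a 20% relative rise fails people with very high or very low craving at the start. The documents do not support that either. They give no range or scoring for the craving measure and do not say whether 20% is a ratio or a share of the scale. The argument would amount to criticising a clinical threshold, which is not the point here.

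On the baseline, the two candidate readings are only 15 minutes apart, and the rule's position after the 1:15 measurement makes that the natural reading to compare.

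What the reply does not remove is the missing step. Compliance with Section 15.0 depends on staff remembering a commitment that the schedule in front of them does not mention, and that its discharge branch passes over.

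**Conclusion.** The point holds as a mismatch between an operational rule and the risk section: the discharge step covers craving, and Section 15.0 covers stress and craving. The universal debrief does not close the gap, because it explains the task without checking or addressing symptoms.

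The size cannot be given as a number. The documents contain nothing from which to estimate how many participants would have lasting stress without a rise in craving. The consequence is confined to the end of the Day 8 visit. The primary outcome, Global Cognitive Ability, is collected on Day 0, and the TSST ratings and cortisol samples used in the planned analyses are complete before discharge, so no estimate or test is affected.

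The conclusion assumes that staff follow the Day 8 schedule as written and that no separate procedure, outside these documents, already adds a stress check. It is a cheap and worthwhile improvement to participant safety, not a flaw in the study's inference.

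**What to change.** Reconcile the Discharge row of the Day 8 schedule in Section 10.0 with the stress-induction paragraph of Section 15.0, so that the discharge step covers the same symptoms as the risk section, stress as well as craving. In the same edit, state which craving score is used and which pre-task reading, 11:40 or 11:55, is the baseline. The trigger, the threshold and the response are for the investigators to set; none is proposed here.

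The cost is a wording amendment and a short extra check before the participant leaves. No new data collection is needed, since the Mood and STAI ratings are already taken at 1:15. Section 10.0 says the TSST procedures are already approved under the parent study, so the team may wish to check whether the same wording is in use there.
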